## 8 STUDY ASSESSMENTS AND PROCEDURES

### 8.1 ENDPOINT AND OTHER NON-SAFETY ASSESSMENTS

*Pre-Screening:* automated lists of consecutive patients admit to participating ICU services are generated using ICD10 codes and calculated APACHE II scores to narrow assessment of eligibility; time frame is within 48 hours of ICU admission; existing information from the patient's EHR will be accessed, obtained and kept as study data under a waiver of HIPAA authorization.

*Screening:* study staff manually screen patient electronic health records to confirm eligibility using established inclusion and exclusion criteria; time frame is 10-14 days from eligibility.

*Recruitment:* study staff contact eligible patient, LNOKs, family members to inform them about the study and ascertain if they are interested and able to participate; time frame is 10-14 days from eligibility.

*Enrollment:* subjects complete informed consent procedures with study staff and are given baseline questionnaires to complete (in person, by mail, by telephone, or online); time frame is 10-14 days from eligibility, however additional family members may be enrolled after this period until 1-month from patient randomization.

*Randomization:* subjects are randomized when a family member's completed baseline questionnaire has been received by the study; time frame is within 1 business day from receipt.

*Intervention:* a communication facilitator (study nurse/interventionist) makes contact with the enrolled subject within 1 business day from randomization; duration of intervention is 3 months, however this may be shorter if the patient dies, or extended if the facilitator finds a need to do so based on her clinical judgement; facilitators have a final contact with participants at the end of the period.

*Control:* subjects are contacted by study staff as the patient's hospital trajectory is monitored; time frame for check-in contacts is at transition out of ICU/to acute care, discharge from hospital, and in the event of patient death (condolence card).

*Follow-up at 1-month:* subjects are contacted by study staff and reminded of the first follow-up questionnaire at 1 month after randomization; reminders are sent at two weeks if questionnaires have not been returned; subjects may also be reminded by phone, email, text for six weeks (one contact per week).

*Follow-up at 3-months:* subjects are contacted by study staff and reminded of the second follow-up questionnaire at 1 month after randomization; reminders are sent at two weeks if questionnaires have not been returned; subjects may also be reminded by phone, email, text for eight weeks (one contact per week).

*Follow-up at 6-months:* subjects are contacted by study staff and reminded of the third follow-up questionnaire at 1 month after randomization; reminders are sent at two weeks if questionnaires have not

been returned; subjects may also be reminded by phone, email, text for eight weeks (one contact per week) and a second reminder questionnaire is sent at the end of the eight weeks.

*Interview:* purposively sampled participants will be contacted by study staff to ascertain their availability and interest in participating in a qualitative interview at the end of their study period.

Chart abstraction: additional data will be collected from the patient's EHR at the end of the study period to evaluate the intervention; existing information from the patient's EHR will be accessed, obtained and kept as study data with HIPAA authorization from patient or the patient's LNO/LAR.

## 8.2 SAFETY ASSESSMENTS

N/A

## 8.3 ADVERSE EVENTS AND SERIOUS ADVERSE EVENTS

### 8.3.1 DEFINITION OF ADVERSE EVENTS

This protocol uses the definition of adverse event from 21 CFR 312.32 (a): any untoward medical occurrence associated with the use of an intervention in humans, *whether or not considered intervention related*.

### 8.3.2 DEFINITION OF SERIOUS ADVERSE EVENTS

The UW IRB definition of Serious Adverse Events is: Any untoward or unfavorable medical occurrence in a human subject, including any abnormal sign (for example, abnormal physical exam or laboratory finding), system, or disease temporally associated with the subject's participation in the research. The research may or may not be causally related to it.

### 8.3.3 CLASSIFICATION OF AN ADVERSE EVENT

#### 8.3.3.1 SEVERITY OF EVENT

For adverse events (AEs), the following guidelines will be used to describe severity.

- **Mild** – Events require minimal or no treatment and do not interfere with the participant's daily activities.
- **Moderate** – Events result in a low level of inconvenience or concern with the therapeutic measures. Moderate events may cause some interference with functioning.
- **Severe** – Events interrupt a participant's usual daily activity and may require systemic drug therapy or other treatment. Severe events are usually potentially life-threatening or incapacitating. Of note, the term "severe" does not necessarily equate to "serious".

#### 8.3.3.2 RELATIONSHIP TO STUDY INTERVENTION/EXPERIMENTAL MANIPULATION

All adverse events (AEs) will have their relationship to study procedures, including the intervention, assessed by appropriately trained clinicians based on temporal relationship and their clinical judgment. The degree of certainty about causality will be graded using the categories below.

- **Definitely Related** – There is clear evidence to suggest a causal relationship, and other possible contributing factors can be ruled out. The clinical event, including an abnormal laboratory test result, occurs in a plausible time relationship to study procedures administration and cannot be explained by concurrent disease or other drugs or chemicals. The response to withdrawal of the study procedures should be clinically plausible. The event must be pharmacologically or phenomenologically definitive.
- **Probably Related** – There is evidence to suggest a causal relationship, and the influence of other factors is unlikely. The clinical event, including an abnormal laboratory test result, occurs within a reasonable time after administration of the study procedures, is unlikely to be attributed to concurrent disease or other drugs or chemicals, and follows a clinically reasonable response on withdrawal.
- **Potentially Related** – There is some evidence to suggest a causal relationship (e.g., the event occurred within a reasonable time after administration of study procedures). However, other factors may have contributed to the event (e.g., the participant's clinical condition, other concomitant events). Although an AE may rate only as "possibly related" soon after discovery, it can be flagged as requiring more information and later be upgraded to "probably related" or "definitely related", as appropriate.
- **Unlikely to be related** – A clinical event, including an abnormal laboratory test result, whose temporal relationship to study procedures administration makes a causal relationship improbable (e.g., the event did not occur within a reasonable time after administration of the study procedures) and in which other drugs or chemicals or underlying disease provides plausible explanations (e.g., the participant's clinical condition, other concomitant treatments).
- **Not Related** – The AE is completely independent of study procedures administration, and/or evidence exists that the event is definitely related to another etiology. There must be an alternative, definitive etiology documented by the clinician.

#### 8.3.3.3 EXPECTEDNESS

A clinician with appropriate expertise in clinician care will be responsible for determining whether an adverse event (AE) is expected or unexpected. An AE will be considered unexpected if the nature, severity, or frequency of the event is not consistent with the risk information previously described for the study procedures.

#### 8.3.4 TIME PERIOD AND FREQUENCY FOR EVENT ASSESSMENT AND FOLLOW-UP

The occurrence of an adverse event (AE) or serious adverse event (SAE) may come to the attention of study personnel during study visits, data collection, reminders or check-in contacts, and/or interviews of a study participant, or upon review by a study monitor.

All AEs, not otherwise precluded per the protocol, will be captured on the appropriate report form. Information to be collected includes event description, time of onset, clinician's assessment of severity, relationship to study procedures (assessed only by those with the training and authority to make a diagnosis), and time of resolution/stabilization of the event. All AEs occurring while on study will be documented appropriately regardless of relationship. All AEs will be followed to adequate resolution.

Changes in the severity of an AE will be documented to allow an assessment of the duration of the event at each level of severity to be performed. Documentation of onset and duration of each episode will be maintained for AEs characterized as intermittent.

Research coordinators will record events with start dates occurring any time after informed consent is obtained until 30 days after the last day of study participation.

#### 8.3.5 ADVERSE EVENT REPORTING

Adverse Events are reported to the UW IRB within 10 business days. Adverse Events are also reported to the Chair of the DSMC, who will make the decision whether to engage the full committee.

#### 8.3.6 SERIOUS ADVERSE EVENT REPORTING

In consultation with the PI, a trained member of the study team will be responsible for conducting an evaluation of a Serious Adverse Event and shall report the results of such evaluation to the NIH, DSMC, and the reviewing Institutional Review Board (IRB) as soon as possible, but in no event later than 10 working days after the investigator first learns of the event.

#### 8.3.7 REPORTING EVENTS TO PARTICIPANTS

N/A

#### 8.3.8 EVENTS OF SPECIAL INTEREST

N/A

#### 8.3.9 REPORTING OF PREGNANCY

N/A

### 8.4 UNANTICIPATED PROBLEMS

#### 8.4.1 DEFINITION OF UNANTICIPATED PROBLEMS

This protocol uses the definition of Unanticipated Problems as defined by the Office for Human Research Protections (OHRP). OHRP considers unanticipated problems involving risks to participants or others to include, in general, any incident, experience, or outcome that meets all of the following criteria:

- Unexpected in terms of nature, severity, or frequency given (a) the research procedures that are described in the protocol-related documents, such as the Institutional Review Board (IRB)-approved research protocol and informed consent document; and (b) the characteristics of the participant population being studied;
- Related or possibly related to participation in the research (“possibly related” means there is a reasonable possibility that the incident, experience, or outcome may have been caused by the procedures involved in the research); and

- Suggests that the research places participants or others at a greater risk of harm (including physical, psychological, economic, or social harm) than was previously known or recognized.

Corrective actions will be taken as needed and advised.

#### 8.4.2 UNANTICIPATED PROBLEMS REPORTING

The investigator will report Unanticipated Problems (UPs) to the reviewing Institutional Review Board (IRB), and the Chair of the DSMC. The Unanticipated Problems report will include the following information:

- Protocol identifying information: PI's name, and the IRB project number
- A detailed description of the event, incident, experience, or outcome
- An explanation of the basis for determining that the event, incident, experience, or outcome represents an Unanticipated Problem
- A description of any changes to the protocol or other corrective actions that have been taken or are proposed in response to the Unanticipated Problem

To satisfy the requirement for prompt reporting, UPs will be reported using the following timeline:

- Unanticipated Problems that are serious adverse events (SAEs) will be reported to the IRB, the DSMC, and to the funding agency within 10 working days of the investigator becoming aware of the event
- Any other Unanticipated Problems will be reported to the IRB and to the DSMC within 10 working days of the investigator becoming aware of the problem
- All Unanticipated Problems should be reported to appropriate institutional officials in accordance with the IRB's receipt of the report of the problem from the investigator and determination of subsequent action.

#### 8.4.3 REPORTING UNANTICIPATED PROBLEMS TO PARTICIPANTS

N/A

### 9 STATISTICAL CONSIDERATIONS

#### 9.1 STATISTICAL HYPOTHESES

- Specific Aim 1, Primary Endpoint  
Hypothesis: The intervention will improve patient and family outcomes, compared to attention control.
- Specific Aim 2, Secondary Endpoint  
Hypothesis: The intervention will improve value by reducing ICU costs, hospital costs and readmissions and improve the cost-consequence ratio for each outcome as compared with attention control.
- Specific Aim 3, Other Outcomes

Anticipated findings: We will identify primary factors associated with key implementation outcomes.

## 9.2 SAMPLE SIZE DETERMINATION

The primary focus for sample size estimation is the primary outcome: mean family member depression over 6 months as assessed by the HADS depression subscale. For all calculations, we assume a two-sided test with a significance level of 0.05. If we assume 300 total family members (1 family member per patient and 150 per arm), a standard deviation of HADS depression scores of 4.2 points in both arms, 3 measurements of depression (at 1,3, and 6 months), and an intraclass correlation (ICC) of 0.2, we will be able to detect a difference in mean depression of at least 0.93 points with 80% power and 1.07 points with 90% power (Power Table Below). These detectable differences at 80% power become 0.86 if the ICC is 0.1 and 1.05 if the ICC is as high as 0.4. If we had only 1 measurement instead of 3 per family member or, equivalently, if the ICC were 1, we would have 80% power to detect a difference of at least 1.36 points. Across all of these varying conditions, detectable differences are slightly within or below estimates of the minimally clinically important difference (MCID) of 1.6 to 2.0 available from the literature, suggesting we will have adequate power to identify a minimally clinically important difference. Although these MCIDs and minimum detectable effects are just estimates, they provide the best available evidence that power will be adequate to detect relatively small but important differences. We anticipate >80% complete data for all outcomes so we will randomize 376 patients to achieve 300 patients and at least 300 family members with complete data. If our response rate is 70%, then we would expect responses for 263 patients and at least 263 family members and with an ICC of 0.2, we would be able to detect a difference in mean depression of at least 0.99 points with 80% power. If we have more than 1 family member per patient (1.5 is expected), we will be able to detect smaller differences at the same power. In addition, we have 80-90% power to detect reasonable effects for other continuous outcomes in Aim 1. For the binary outcome of goal-concordance care, we have about 80% power to detect a difference in proportion concordant of 0.6 and 0.7, with 3 measurements from each of 300 total participants and an ICC of 0.13; the estimate of 0.6 for the controls is from a prior study and our preliminary data. We targeted power to identify differences within or slightly less than available estimates of “minimally important clinical differences” so that we would be confident that we would be powered to detect a minimally important clinical difference.

Power Table: Range of minimum detectable effects with 80%- 90% power for HADS

OUTCOME MEASURE	Range of Minimum Detectable Effects* (†MCID if known)	Standard deviation 
HADS depression subscale	0.86 – 1.3 (†1.6-2.0)	4.2
HADS anxiety subscale	0.97 – 1.47 (†1.6-2.0)	4.75
HADS total score	1.69 – 2.56 (†1.6-2.0)	8.25

\*Range due to: intraclass correlation (0.1-0.4), response rate (70% or 80%), and power (80% or 90%); †MCID = estimates of minimal clinically important difference

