### 3 OBJECTIVES AND ENDPOINTS

OBJECTIVES	ENDPOINTS	JUSTIFICATION FOR ENDPOINTS
Primary		
Assessing family member symptoms of depression over time, from baseline through 6 months	Family member symptoms of depression assessed with the Hospital Anxiety and Depression Scale (HADS-D) subscale	The HADS has become standard for ICU and post-ICU studies. It is a reliable and valid 14-item, 2-domain (anxiety and depression) tool used to assess symptoms of psychological distress. Seven items evaluate depression. Each item is scored on a 4-point scale (ranging from 0-3) with scores ranging from 0-21. HADS has been used in over 700 studies with evidence of reliability, validity and responsiveness among critically ill patients and their family.
Secondary		
Assessing family member symptoms of anxiety over time, from baseline through 6 months	Family member symptoms of anxiety assessed with the Hospital Anxiety and Depression Scale (HADS-A) subscale	The HADS has become standard for ICU and post-ICU studies. It is a reliable and valid 14-item, 2-domain (anxiety and depression) tool used to assess symptoms of psychological distress. Seven items evaluate anxiety. Each item is scored on a 4-point scale (ranging from 0-3) with scores ranging from 0-21.
Goal-concordant care	Concordance between the care patients want and the care they are receiving will be measured with two questions from the SUPPORT study. The first defines patients' preferences: "If the patient had to make a choice at this time, would the patient prefer a course of treatment focused on extending life as much as possible, even if it means having more pain and discomfort, or would the patient	The outcome is a dichotomous variable of whether the preference matches the report of care received. Although this creates a "false dichotomy" in that many patients want both, this "forced choice" helps identify patients' top priority. Based on prior studies, we expect only 50-60% of controls will report goal-concordant care. Items completed by family respondents.

OBJECTIVES	ENDPOINTS	JUSTIFICATION FOR ENDPOINTS
	want a plan of care focused on relieving pain and discomfort as much as possible, even if that means not living as long?" The second question assesses perceptions of current treatment using the same two options.	

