- Concordance between the care patients want and the care they are receiving will be measured with two questions from the SUPPORT study. The first defines patients’ preferences: “If the patient had to make a choice at this time, would the patient prefer a course of treatment focused on extending life as much as possible, even if it means having more pain and discomfort, or would the patient want a plan of care focused on relieving pain and discomfort as much as possible, even if that means not living as long?” The second question assesses perceptions of current treatment using the same two options. The outcome is a dichotomous variable of whether the preference matches the report of care received. Although this creates a “false dichotomy” in that many patients want both, this forced choice helps identify patients’ top priority. – initial and follow-up surveys
- Single-Item health status question (SF-1): “In general, would you say your health is: Excellent, Very good, Good, Fair, Poor” – initial survey and follow-up surveys
- Single-Item health status question (SF-1): “In general, would you say your family member/friend’s health is: Excellent, Very good, Good, Fair, Poor” – initial survey and follow-up surveys (proxy for patient)
- FRAIL scale (Fatigue, Resistance, Ambulation, Illnesses, & Loss of Weight) – initial survey and follow-up surveys (proxy for patient)
- Preferred Role in Decision-Making – initial survey and follow-up surveys
- Perceived Competence Scale (PCS) – initial and follow-up surveys
- Impact Of Events Scale-Revised (IES-6) – follow-up surveys
- Measuring the Quality of Life of Seriously Ill Patients (QUAL-E FAMILY) – initial and follow-up surveys
- Comprehensive Score for Financial Toxicity (modified FACIT-COST) – follow-up surveys

- Healthcare Utilization – follow-up surveys (proxy for patient)
- Intervention Assessment – follow-up surveys (intervention arm only); and
- demographic items, including social support and health literacy (single item).

Family of patients who die will receive after-death questionnaires at the usual schedule but at least 4 weeks after the patient's death. The after-death questionnaire contains: decision-making, FACIT-COST, QUAL-E FAMILY (revised), HADS, IES-6, SF-1 and demographic items.

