### 5 STUDY POPULATION

#### 5.1 INCLUSION CRITERIA

##### --PATIENTS--

Eligible patients will be those who are 18 years of age or older, English-speaking, with a chronic life-limiting illness suggesting a median survival of approximately 2 years or a severe acute illness with a risk of hospital mortality of at least 15%.

- Chronic life-limiting illnesses include:
  - cancer with a poor prognosis (e.g. metastatic cancer);
  - chronic pulmonary disease (e.g. COPD or restrictive lung disease);
  - coronary artery disease (CAD);
  - congestive heart failure (CHF);
  - peripheral vascular disease (PWD);
  - severe liver disease (e.g. cirrhosis);
  - diabetes with end-organ damage;
  - renal failure; and
  - dementia.
  - We will also include patients who are ventilator-dependent (receiving long-term mechanical ventilation) and have been admitted from a long-term acute care (LTAC) facility.
- Acute illness criteria include APACHE II (alternately SOFA or trauma severity) score predicting a 15% or greater risk of hospital mortality.
- Acute illnesses and conditions include:
  - acute respiratory distress syndrome (ARDS) with P/F ratio <=300;
  - on extracorporeal life support (ECLS or ECMO);
  - cardiopulmonary arrest, with Glasgow coma score  $\leq 12$ ;
  - subarachnoid hemorrhage (SAH) Fisher grade 3/4 with Glasgow coma score  $\leq 12$ ;
  - spontaneous hemorrhage (ICH, IPH, EDH, SDH) with Glasgow coma score  $\leq 12$ ;
  - stroke or cardiovascular accident (CVA) with Glasgow coma score  $\leq 12$ ;
  - decompressive/crash craniotomy (bone flap) with Glasgow coma score  $\leq 12$ ;
  - traumatic brain injury (TBI) or diffuse axonal injury (DAI) based on MRI ~day 10; or
  - anoxic brain injury due to cardiac arrest >48 hours;
  - or acute respiratory failure requiring invasive mechanical ventilation.
  - We will also include patients with: new spinal cord injury causing quadriplegia, and confirmed COVID-19 who are admitted to the ICU.
- If patients do not have decisional capacity and have no legal surrogate decision-maker to provide consent, they will not be eligible for participation.

--FAMILY--

Eligible family subjects will be those who are 18 years of age or older, English-speaking, and identified by the patients as someone they would want involved in his or her medical care or decision-making.

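### The 80% power for goal-concordant care in Section 9.2 assumes three answers from every relative, but answers stop when the patient dies; on the plan's own one-relative basis power is about 70-77%

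*Combined protocol and SAP*

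**What the plan says.** Section 9.2 sets the framework for all its calculations: "we assume a two-sided test with a significance level of 0.05", 150 relatives per arm, one per patient. For goal-concordant care it claims "about 80% power to detect a difference in proportion concordant of 0.6 and 0.7, with 3 measurements from each of 300 total participants", with "an ICC of 0.13; the estimate of 0.6 for the controls is from a prior study and our preliminary data". On completeness it says "We anticipate >80% complete data for all outcomes", and it randomizes 376 patients to obtain 300. For HADS depression it also works through a 70% response rate (263 relatives) and several ICCs. For goal concordance it gives a single figure.

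Other sections bear on that figure:

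- Section 4.1 puts the two concordance questions on the initial and follow-up surveys. For bereaved relatives: "The after-death questionnaire contains: decision-making, FACIT-COST, QUAL-E FAMILY (revised), HADS, IES-6, SF-1 and demographic items". The concordance questions are not listed. The same section says this form takes the place of the next follow-up questionnaire and that later forms are shortened.
- Section 5.1 admits patients through a chronic illness with a median survival of about 2 years, or through "a severe acute illness with a risk of hospital mortality of at least 15" percent.
- Section 3 states for this outcome that "we expect only 50-60% of controls will report goal-concordant care".

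**The concern.** The two concordance questions ask what the patient would prefer now and what the current treatment aims at. They have no meaning after death, and the after-death form does not carry them. The decision-making entry on that form is not a substitute, because Section 4.1 lists preferred decision-making role separately from concordance. A relative whose patient dies before month 1 therefore contributes no follow-up answer on this outcome, and one whose patient dies between months 1 and 3 contributes one.

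The population is selected for high mortality, yet the power statement counts three answers from all 300 relatives. It also uses 0.6 for controls, the end of the plan's 50-60% range that gives the higher power for a 10-point difference. Goal-concordant care appears in the trial's title, and Section 4.2 treats it as a key outcome. A null result on it would be read against the stated 80%.

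**Working it through.** **Inputs from the documents.** Two-sided 0.05; 150 relatives per arm, or 263/2 = 131.5 at 70% response; 0.6 versus 0.7; ICC 0.13; three measurements (all Section 9.2). Control range 50-60% (Section 3). Entry mortality of at least 15% in hospital, or median survival of about 2 years (Section 5.1).

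**Assumptions.** The documents give no death rates at 1, 3 or 6 months, so two patterns are built from the entry criteria:

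- (a) Exponential survival with a 24-month median: dead by month m = 1 - 2^(-m/24), which is 2.8%, 8.3% and 15.9% at months 1, 3 and 6.
- (b) 15% lost before month 1 and none later.

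**Formulas.** A relative with k answers contributes k/(1 + (k-1) x ICC). The effective number per arm, n_eff, is the number of relatives per arm times the mean contribution. Power = Phi(|p2 - p1| x sqrt(n_eff/(p1q1 + p2q2)) - 1.96).

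**The plan's own figure.** 3/(1 + 2 x 0.13) = 2.381, and 150 x 2.381 = 357.1. The variance term is 0.24 + 0.21 = 0.45. Then 0.1 x sqrt(357.1/0.45) = 2.817, and Phi(0.857) = 80.4% (80.1% with a pooled variance). The same weighting gives the plan's 0.93 points for HADS depression at ICC 0.2, so this is evidently the method used.

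**With deaths, one relative per patient.**

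- (a) Mean contribution = 0.841 x 2.381 + 0.076 x 1.770 + 0.055 x 1 = 2.191, so n_eff = 328.7.
- (b) 0.85 x 2.381 = 2.024, so n_eff = 303.6.

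| ICC 0.13 | 0.6 vs 0.7 | 0.5 vs 0.6 |
|---|---|---|
| No deaths | 80% | 77% |
| (a) 2-year median | 77% | 74% |
| (b) 15% before month 1 | 74% | 70% |
| (a) and 70% response | 72% | 68% |
| (b) and 70% response | 68% | 64% |

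For 0.5 versus 0.6 the variance term is 0.25 + 0.24 = 0.49. At 80% power, 150 per arm and controls at 0.6, the detectable difference is 10.3 points under (a) and 10.7 under (b).

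**ICC.** With no deaths and 0.6 versus 0.7, power is 76% at ICC 0.2 and 65% at 0.4. It passes below 80% at ICC 0.137.

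**With 1.5 relatives per patient.** Multiply n_eff by 1.5/(1 + 0.5r), where r is the assumed correlation between the mean answers of relatives of one patient. For r = 0.2 to 0.8 the factor is 1.364 to 1.071. At 150 patients per arm and ICC 0.13:

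| | 0.6 vs 0.7 | 0.5 vs 0.6 |
|---|---|---|
| (a) | 80-88% | 76-86% |
| (b) | 77-86% | 73-83% |

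**Completeness.** If 15% lose the item through death, overall completeness of 80% needs 0.80/0.85 = 94% response among the remaining relatives.

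**The case against.** The strongest reply is that the plan has slack it did not use. It expects 1.5 relatives per patient (564/376) and did not count them in the 80%. Under the death patterns above, that restores power to near or above 80% for 0.6 versus 0.7 over most of the assumed correlation range. This stands, and it is why one cannot say that the trial lacks 80% power. It does not rescue the sentence as written, which rests on one relative per patient, and Section 9.2 gives no between-relative correlation with which to claim the gain.

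A second reply is that the 376-to-300 allowance already covers deaths. Section 9.4.1 names death among the sources of missing data, and with 15% dead about 320 of 376 patients would still be alive. Section 9.2 does not say either way. A reader might infer that the completeness figure cannot hold for this outcome. The documents support less: it would require about 94% response among relatives of survivors, in a section that also plans for 70% response.

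Third, mortality risk at entry is not mortality after randomization. Patients with withdrawal of life support pending are excluded (Section 5.2), and randomization waits for a completed baseline questionnaire (Section 8.1). Deaths before randomization cost nothing, so pattern (b) may overstate early loss. Patients with at least 15% predicted hospital mortality may equally have more deaths over 6 months. The documents do not settle which.

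Finally, the outcome is secondary, and the plan says only about 80%. Both are true, and they limit the weight of the point.

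**Conclusion.** The point holds in a limited form. The stated 80% is computed correctly on a basis that the design cannot supply. On that same one-relative basis at ICC 0.13, power is about 74-77% for 0.6 versus 0.7 and 70-74% for 0.5 versus 0.6, and 64-72% across both if response is 70%. These figures rest on an assumed survival shape (a) or assumed timing of loss (b). Counting 1.5 relatives per patient at 80% response gives about 77-88% for 0.6 versus 0.7 and 73-86% for 0.5 versus 0.6, resting on an assumed correlation of 0.2-0.8.

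A reader might infer that the real power is in the mid-50s. The documents do not support that. Reaching 54% takes, for example, mortality of 20%, 27% and 33% at 1, 3 and 6 months together with ICC 0.4. That mortality appears nowhere in the protocol, and the 0.1-0.4 range is given for HADS, while 0.13 is given for this outcome. Nor is the trial as a whole underpowered on this account: the primary outcome is HADS depression, and HADS is on the after-death form. Severity is minor to moderate.

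**What to change.** In Section 9.2:

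1. Replace the single power figure for goal-concordant care with a sensitivity range based on the answers expected while the patient is alive. State the death assumptions, and cover control rates of 0.5 to 0.6, both response rates, a range of ICCs, and 1 and 1.5 relatives per patient with a stated between-relative correlation. The sponsor should compute the range over the full grid it chooses; the tables above cover only ICC 0.13 under two death patterns.
2. Say whether the 20% allowance for incomplete data includes deaths, and limit the statement of more than 80% complete data to outcomes carried on the after-death form.

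The cost is a short recalculation and rewording of one section. The sample size, data collection and primary analysis do not change. The downside for the sponsor is that a stated figure becomes slightly less favourable.
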